DASS-21	Depression Anxiety and Stress Scales
DSMC	Data Safety Monitoring Committee
FCR	Fear of Cancer Recurrence
FCRI	Fear of Cancer Recurrence inventory
FDA	Food & Drug Administration
GCP	Good Clinical Practice
GP	General Practitioner
HREC	Human research ethics committees
ICF	Informed consent form
ICH GCP	International Conference on Harmonisation of Good Clinical Practice
ID	Identification
IELab	Australian Industrial Ecology Virtual Laboratory
Kg	Kilogram
M	Million
MASC Trials	Melanoma and Skin Cancer Trials Ltd.
MM	Millimetre
MIA	Melanoma Institute Australia
NMSC	Non-Melanoma Skin Cancers
RCT	Randomised Controlled Trial
SEIFA	Socio-Economic Indexes for Areas
SSE	Skin Self-examination
TMC	Trial Management Centre
USYD	University of Sydney

197

198

199

200

201

202

203

204

205

206

207

208

209

210

211

212

213

214

215

3. Study synopsis

Title:	A pilot randomised controlled trial of patient-led surveillance compared to clinician-led surveillance in people treated for localised melanoma
Study Number:	02.17 MEL-SELF
Primary Objective:	1. To assess the feasibility of patient-led surveillance.
Rationale:	Most new (and recurrent melanomas) are detected by patients or family members in between scheduled visits, and this might be increased with additional training and support for patient skin self-examination and with Teledermatology assessment of patient-detected abnormalities. This may enable less frequent scheduled follow-up with melanoma clinicians. Fewer scheduled visits may be just as safe, cause less anxiety and consume fewer resources.
Study Design:	Randomised Controlled Trial (RCT)
Sample Size (by treatment group):	50 participants allocated to the intervention group and 50 participants allocated to the usual care group
Study Arms (Intervention and Control):	
Intervention group:
 
 (i) Patient-led surveillance: web-based questionnaire based on the ASICA skin checker App (with instructional videos and electronic reporting of lesions discovered on skin self-examination), Smartphone App for participants to perform teledermoscopy with feedback to participants of Dermatologist report, email/SMS reminders to perform total skin self-examination every 2 months; (ii) An educational booklet. (iii) Usual scheduled follow-up; (iv) Unscheduled visits as needed 
Control group:
 
 (i) an educational booklet (ii) Usual scheduled follow-up ; (iii) Unscheduled visits as needed
Study Population	Adult patients who are undergoing routine melanoma skin cancer surveillance.
Study Endpoints (Primary and Secondary):	
 1. Primary outcome: Proportion of patients who are contacted and invited to participate, who are finally randomised in the trial. 2. Secondary outcomes: Adherence with recommended skin self-examination practice (total body self-examination conducted two- monthly), thoroughness, confidence, knowledge attitudes and beliefs about skin self-examination, fear of new or recurrent melanoma, general anxiety, stress and depression, number of lesions surgically excised, number of follow up visits attended (both scheduled and unscheduled), inter-dermatologist reliability of teledermoscopy, resource use and costs (both financial and carbon emission costs), and results from the qualitative sub-study.

216 **4. Project Team Roles and Responsibilities**

217 **Study Chair:**

218 [name], Senior Lecturer in Clinical Epidemiology, Public Health, School of Public Health, The
219 University of Sydney.

220

221 **Protocol Development Group:**

222 [name] (academic health psychologist)
223 Associate [name] (cancer epidemiologist)
224 Associate [name] (statistician)
225 [name] (clinical epidemiologist)
226 Associate [name] (academic dermatologist)
227 Associate [name] (melanoma surgeon)
228 Associate [name] (academic dermatologist)
229 [name] (academic dermatologist)
230 [name] (epidemiologist & health economist)
231 [name] (academic health psychologist)
232 Associate [name] (melanoma health economist)
233 [name] (consumer investigator)
234 [name] (consumer investigator)
235 [name] (public health researcher)
236 [name] (health economist)

237

238 **5. Introduction and rationale**

239 **5.1. Background**

240 The increasing incidence of melanoma in Australia (~500% increase from 3,526 new melanomas in
241 1982 to 17,570 by 2020)¹ is largely driven by increased early detection of localised melanoma
242 before it has spread from the skin². After treatment, these patients are at risk of developing a
243 recurrent or new primary melanoma and/or NMSCs and are recommended to undergo lifelong
244 follow-up at intervals based on stage that range between 3 to 12 months³. However, they have a
245 very good prognosis in terms of life expectancy: the same as the general population for melanoma
246 in situ (stage 0), and 96% 20 year survival for thin melanomas (<1 mm) (together these are >80%
247 of all localised melanomas⁴). The potential benefits of clinician surveillance for recurrent or new
248 primary melanoma and NMSC in ensuring timely treatment, needs to be balanced against costs
249 and possible physical and psycho-social harms of frequent scheduled follow-up clinic visits and
250 investigations^{5,6}. The costs of follow-up are substantial and have been estimated at AU\$44M over
251 5 years for American Joint Committee of Cancer (AJCC) stage I/II⁷. There are also opportunity
252 costs in terms of clinician time, with waiting lists for new patients in public dermatology clinics
253 potentially getting longer. Fewer scheduled follow-up visits may have little impact on the detection
254 of recurrence and new primaries⁸ and can result in substantial cost savings⁹. Clinicians are more
255 likely to choose this option if they are confident in the patient's ability to do their own surveillance
256 through skin self-examination (SSE)¹⁰.

257 Currently there is no evidence that frequent scheduled follow-up has any effect on patient
258 survival¹¹. In contrast, there is evidence that self-detection of recurrence is associated with higher
259 survival compared to detection by a clinician, highlighting the importance of patient vigilance. Yet
260 despite SSE being universally recommended by clinical guidelines, education and practice remains
261 suboptimal, with less than half of respondents in a study of melanoma patients in NSW [paper
262 currently under review], and only 14% in an American study¹², indicating that they examined all
263 parts of the body. In fact current evidence suggests that few people carry out SSE thoroughly, with
264 many failing to view hard-to-see areas, seeking assistance by a partner, or documenting lesions
265 that they need to check again to notice changes¹³.

266

267 5.2. Justification/ Significance

268 This pilot study is the first to evaluate the feasibility of patient-led surveillance through: Web-based
269 version of the 'ASICA skin checker' App (instructional videos, guided self-examination and
270 electronic reporting), Smartphone App using teledermatology of patient detected lesions (detailed
271 images transmitted electronically for dermatology review), email + SMS reminders + educational
272 booklet + scheduled and unscheduled clinic visits. It will support planning for a large trial to
273 compare the effects of patient-led surveillance and clinician-led surveillance on health outcomes,
274 psychological outcomes and resource use. The larger study will aim to demonstrate that patient-
275 led surveillance results in health outcomes that are at least as good as clinician-led surveillance,
276 with better psychological outcomes and less health resource use. Our work will allow for evidence-
277 based follow-up after treatment of localised melanoma, to maximise patient wellbeing and the early
278 detection of new or recurrent melanoma, while minimising costs to the health system.
279

280 5.3. Lay summary

281 **Background and Aim:** Most melanomas are detected by patients or family members between
282 scheduled visits; Even more might be detected if patients are trained in how to self-examine their
283 skin and have access to timely dermatology review. Frequent follow-up of localised melanoma is
284 time and resource intensive and has not shown improved outcomes. This pilot study, and the larger
285 one that will follow, aim to provide evidence on the best model of follow-up care after treatment for
286 localised melanoma.

287 **Research Design:** This proposal is for a pilot randomized controlled trial among patients who have
288 had surgery for localised melanoma and are followed up at recruiting skin cancer specialist clinics
289 or general practice clinics. We will compare the effects of offering patient-led surveillance (Web-
290 based version of the ASCIA skin checker + dermatoscope + Teledermatology + email and text
291 reminders to support self-examination + an educational booklet + scheduled and unscheduled clinic
292 visits) to clinician-led surveillance (an educational booklet + scheduled and unscheduled clinic
293 visits). We will document how well participants are able to perform self-examination, their levels of
294 melanoma-related anxiety, the number of skin lesions biopsied or removed, and the costs of follow-
295 up to the participant, to the healthcare system, and to the planet (in the form of carbon emission
296 costs). We will recruit 100 people who have been treated for a first primary localised melanoma,
297 own a smartphone, and are being followed up at a recruiting skin cancer specialist clinic or general
298 practice clinic. Potential participants will be screened in clinic by the treating clinician. Potential
299 participants will be given the study invitation package either in clinic or by mail out. Patients who
300 are found to be eligible and who consent to participate will be randomised to patient-led
301 surveillance or clinician-led surveillance. Participants will be sent questionnaires at six months to
302 measure outcomes using paper or online surveys. We will also collect data through the web-based
303 version of the ASICA skin checker (in the intervention group), patient diaries (to measure out of
304 pocket costs), and from the clinic databases (including follow-up visits, surgical procedures and
305 pathology reports of any skin lesions removed).

306 6. Study design

307 6.1. Research question(s)/ aim(s):

308 The **primary aim** of the study is to investigate whether patient-led surveillance (Web-based version
309 of the ASICA skin checker + smartphone App and dermatoscope attachment + Teledermatology +
310 email/SMS reminders) is feasible.

311 The **secondary aims** are to investigate whether patient-led surveillance:

- 312 1. increases patients' adherence with recommended SSE practice (total body self-examination
313 conducted two- monthly)
- 314 2. improves confidence in, knowledge of, attitudes and beliefs about, skin self-examination,
- 315 3. decreases level of fear of new or recurrent melanoma, general anxiety, stress and
316 depression,

- 317 4. decreases the number of lesions surgically excised, the number of follow up visits attended
318 (both scheduled and unscheduled), resource use and costs and carbon emissions (costing
319 study)
320 5. Increases acceptability of reducing scheduled clinic visit frequency
321 6. has acceptable inter-rater reliability for the Teledermatology assessment (reliability sub-
322 study)
323 7. is accepted by clinicians and patients views (qualitative sub-study)
324

325 6.2. Study design

326 This study is a 2-armed RCT with 1:1 allocation to intervention vs the control group, with a
327 Teledermatology repeatability sub-study nested within the intervention arm to estimate the inter-
328 rater reliability of Teledermatology.
329

330 In addition, we will conduct a costing study to estimate the total costs to the health system, to
331 patients, and to the planet (carbon emissions) for the intervention and control groups. All costs
332 associated with SSE, skin surveillance and management of newly identified lesions, out-of-pocket
333 costs and opportunity costs will be included. We will also measure and value all resources used
334 (micro-costing approach) to estimate the carbon emissions associated with melanoma surveillance
335 for the intervention and control groups.

336 We will conduct a qualitative sub-study to understand patients' and clinicians' acceptability and
337 satisfaction with the intervention and explore components which may need to be changed. The
338 qualitative evaluation will be in the form of phone or face to face interviews at the end of the 6
339 month follow-up.
340

341 7. Study population

342 We will recruit adult participants who have been treated for a first primary melanoma, stage 0/I/II,
343 and who are undergoing regular melanoma follow-up at recruiting melanoma and skin cancer
344 clinics in NSW.
345

346 This pilot study aims to recruit 100 patients from the Melanoma Institute Australia (MIA) and Royal
347 Prince Alfred Hospital (RPAH) (specialist treatment centres) and the Newcastle Skin Check clinic
348 (GP run clinic). Recruitment will be done over six months.
349

350 7.1. Inclusion Criteria

- 351 • Patients treated for stage 0/I/II melanoma who are attending regular melanoma follow-up as
352 indicated by scheduled or recommended visit within next 12 months.
353 • Are able to self-examine;
354 • Have a suitable study partner (spouse, partner, family member, friend) to help with self-
355 examination
356 • Own a compatible Smartphone (and have access to Wifi / email / SMS text messaging);
357 • Are able to give informed consent;
358 • Have sufficient English language skills to read the materials and complete the
359 questionnaires;
360 • Aged 18+ years old.

361 7.2. Exclusion Criteria

- 362 • unable to perform self-examination
363 • Patient who currently or previously have had stage III/IV melanoma
364 • Patients with a known past or current diagnosis of cognitive impairment

365 8. Study procedures

366 8.1. Enrolment procedure

367 All patients treated for localised melanoma who are attending regular follow-up, will be identified in
368 clinic by the clinician. The potential participant will be contacted by a research coordinator who will
369 explain the study and give the patient an invitation package either in person or by mail. The initial
370 study invitation package includes: Study Invitation Letter, Participant Information Sheet, Consent
371 Form, Participation Card, Baseline Questionnaire (to measure demographics, knowledge, attitudes
372 and confidence on self-examination and smartphone Apps, and their baseline level of fear of new
373 or recurrent melanoma (using a melanoma specific version of the Fear of Cancer Recurrence
374 Inventory Severity subscale)¹⁴ and reply paid envelope. The letter of invitation will be printed on the
375 clinic letterhead and will be signed by patients' treating clinician, preferably as original signatures
376 but alternatively using electronic signatures with their permission. Participants will be able to opt
377 into the study by returning the signed consent form and participation card to the researchers by
378 reply paid mail or to decline study participation by returning the participation card, or by phone or
379 email. Potential participants will be asked to indicate whether they meet each of the inclusion
380 criteria (e.g. own a compatible Smartphone etc.) and to specify on their participation card how they
381 would like to receive the study dermatoscope and questionnaires reminders (on Text SMS or
382 email). Participants who do not return their consent form or participation card within two weeks will
383 be contacted via telephone by the research staff. If the participant does not return their consent
384 form after this telephone call, no further contact will be made. Participants that do not respond will
385 be recorded as screen fails. The clinic staff will be informed which patients have agreed to
386 participate in the study.

387
388 Consenting participants will then be sent a baseline package in the mail.

389 8.2. Stratification and Randomisation

390 Patients will be stratified by the following factors:

- 391 • AJCC Melanoma Stage (0, IA, IB, IIA, IIB/IIC)
- 392 • Sex/gender (male/female)
- 393 • Age group (18–40, 40–60, 60+)
- 394 • Clinic type (GP clinic/specialist clinic)

395
396

397 Patients will be randomised 1:1 taking into account the above listed stratification factors using a
398 randomisation to one of two study arms:

399 Randomisation will be performed using the offsite randomisation service provided by the NHMRC
400 Clinical Trials Centre, The University of Sydney, thus ensuring allocation concealment. The
401 research coordinator will call the NHMRC Clinical Trials Centre (using their telephone
402 randomisation service) to randomise the patient once a consent form and the baseline
403 questionnaire has been received. Consenting patients who meet all inclusion/exclusion criteria will
404 be randomised in a ratio of 1:1 to the intervention or usual care.

405
406

Full instructions on how to randomise patients are described in the Operations Manual.

407 8.3. Interventions/ Groups

408 Participants allocated to the intervention will receive:

- 409 • An educational booklet 'Your guide to early melanoma',
- 410 • Web-based ASICA skin checker log-in. The web-based ASICA skin checker combines
411 instructional videos, guided total skin self-examination and electronic reporting,¹⁵
- 412 • A dermatoscope to attach to their phone similar to that reported in *Manahan et al.*¹⁶.
- 413 • Detailed written instructions on how to use the smartphone App and dermatoscope.

- 414 • Video outlining how to use the dermatoscope and associated App/online submission
 415 platform.
 416 • Email or SMS text reminders every 2 months to perform SSE.
 417 • Teledermoscopy: participants are required to take dermoscopic images of at least 3 lesions
 418 and up to 9 lesions on each SSE, including all lesions that concern them, and submit these
 419 through the smartphone App. They are also required to enter a text description of the results
 420 of SSE for each part of the body and submit this through the web-based ASICA skin
 421 checker. Both dermoscopic images and text reports will be sent securely to one of the study
 422 dermatologists, who will undertake teledermatology review within 3 days and feedback the
 423 results to the participant.
 424 • Unscheduled visits as needed in addition to those prompted through Teledermatology.
 425 • Scheduled visits as per treating clinician.
 426

427 Those allocated to the control arm will receive:

- 428 • An educational booklet 'Your guide to early melanoma';
 429 • Unscheduled visits as needed
 430 • Scheduled visits as per treating clinician
 431

432 All participants will receive two study questionnaires; one at baseline and one at 6 months.
 433

434 **8.4. Blinding**

435 Blinding of participants, site staff and treating clinicians will not be possible in this trial. Where
 436 possible, outcome assessment will be done masked to study group allocation.
 437

438 **8.5. Duration of treatment/ Study**

439 Unless the study is closed prematurely, it will proceed to the pre-defined accrual target. Following
 440 announcement of closure to recruitment by the research team, no further enrolment will be
 441 possible. It is anticipated, based on estimates from individual sites that the accrual target will be
 442 reached over a period of 6 months. Each participant will be followed up for 6 months. The timeline
 443 below provides an outline of anticipated study milestones:
 444
 445

Timeline	2017	2018	2019	2020
Apply for ethics approval and preparation of study materials	■	■		447 448 449
Recruitment & random allocation		■	■	
6 month follow-up data collection and entry			■	
Analysis of 6 months follow up data finalised and paper drafted				■
Qualitative phone interview study				■
Costing study				■
Data cleaning, statistical and cost analyses				■
Paper & Dissemination				■

463

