665 (including paid and unpaid work), travel costs and carer costs. The diary will be based on existing
666 resource use questionnaires resource use recorded in databases.

667 **(M9) Qualitative results:** We will carry out face-to-face or telephone interviews with a sub-set of
668 intervention group participants at 6 months after randomisation to explore in depth patients'
669 experiences with digitally supported self-examination. We will also interview clinicians to explore
670 their experience of the benefits and limitations of the intervention.

671 **12.3. Potential confounders and biases**

672 **(M10) Demographic and other risk factors including:**

673 Age, sex, ethnicity, Indigenous status, language spoken, marital status, children, occupation,
674 income, highest education level, postcode/SEIFA, brand of smartphone owned (if applicable),
675 baseline use of digital technology/ internet, and personal history of depression or anxiety. We will
676 collect these data using standardised items from the Australian Census questionnaire and other
677 instruments, where appropriate.

678 Clinical characteristics of the index melanoma including AJCC sub-stage and site, retrieved from
679 administrative datasets at the clinics.

680 **13. Statistical methods**

681 **13.1. Sample size and justification**

682 A sample size of 100 participants, with 1:1 allocation to intervention vs control groups, will ensure
683 that the 95% confidence interval for the proportion of potential participants who are recruited has a
684 margin of error of <10% (assuming that 30% of contacted, eligible participants are recruited).

685
686 A sample size of 30 participants in the qualitative sub-study is a well-accepted sample size in
687 qualitative studies using in-depth interviews.¹⁸
688

689 **13.2. Feasibility**

690 Administrative data from our main clinic (MIA) indicates that approximately 800-900 patients are
691 treated for localised melanoma at MIA each year and approximately 50% then attend regular
692 follow-up at MIA.¹⁹ Recruiting 100 patients over 6 months from all patients treated for localised
693 melanoma who are attending follow-up at MIA and the clinic in Newcastle, is highly feasible.

694

695 13.3. Early stopping

696 There are no safety endpoints or criteria for early study termination.

697

698 13.4. Analyses plan**699 13.4.1. Statistical analysis for primary endpoint**

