765 will do this using data from the Australian Industrial Ecology Virtual Laboratory (IELab), which offers
766 a unique platform for the compilation of customized economic input-output tables for the Australian
767 economy. As a first step, we will couple these economic tables with data on carbon emissions for
768 every economic sector. Next, we'll use these integrated tables to undertake well-established input-
769 output mathematical calculations to estimate the direct impacts, as well as the indirect impacts
770 throughout the infinite supply chains of a product, for example. As opposed to conventional life
771 cycle assessments that are affected by so-called truncation errors because they only take into
772 account selected supply chains, input-output analysis considers the entire supply chain of a
773 product, technology or an organization in question, and this provides a complete picture of the
774 impacts.

776 **Qualitative sub-study (intervention group only)**

777 We will conduct a qualitative evaluation after the 6 month follow up among a sub-sample of patients
778 and clinicians. We will invite participants who were randomised to the intervention to indicate their
779 interest in taking part in a interview (number of participants=30) to explore in depth their
780 experiences with digitally supported self-examination. We will carry out face-to-face or telephone
781 interviews among these patients at 6 months after randomisation. Interviews will be audio recorded
782 and transcribed verbatim. We will also interview participating clinicians (n=5-10) to explore their
783 experience of the benefits and limitations of the intervention. The study will take a
784 Phenomenological perspective and will use Framework Analysis,²³ a matrix based method of
785 thematic analysis which has been used successfully in numerous screening studies.^{24,25}

786 **13.6. Missing data**

787 Missing data will be imputed in analysis as appropriate.

788 **13.7. Deviations from original statistical plan**

789 The version of this document and the statistical analyses plan will be updated with each change,
790 and each change noted.

791

792 **14. Responsibilities of the Principal Investigator at each site**

793

794 The study will be performed in accordance with the CPMP/ICH Note for Guidance on Good Clinical
795 Practice (CPMP/ICH/135/95) in Australia and applicable guidelines in participating sites overseas.

796

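### Patient interviewees are recruited by expressed interest with no sampling by use of the package, so people who stopped using it may be under-heard and patient acceptability may look better than it is

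*Combined protocol and SAP*

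**What the plan says.** Section 6.1 lists as aim 7 whether patient-led surveillance "is accepted by clinicians and patients views (qualitative sub-study", so it names this sub-study as the source of the answer. Section 6.2 adds a second purpose, to look at "satisfaction with the intervention and explore components which may need to be changed".

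The rule for finding patients is in section 13.5 (Qualitative sub-study): "We will invite participants who were randomised to the intervention to indicate their" "interest in taking part in a interview (number of participants=30) to explore in depth their" experiences. The interviews take place 6 months after randomisation. The same paragraph adds clinicians: "We will also interview participating clinicians (n=5-10) to explore their" experience of what the intervention does well and where it falls short.

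Section 13.1 justifies the number by convention: "A sample size of 30 participants in the qualitative sub-study is a well-accepted sample size in" studies of this kind. Outcome M9 in section 12.2 speaks only of a subset of the intervention group.

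**The concern.** Each round asks a lot of the participant. Sections 8.3 and 10.1 require a text entry for every part of the body and dermoscopic images of at least 3 lesions, every 2 months. Section 5.1 itself reports that few people do skin self-examination thoroughly. Some drop-off in use is foreseeable.

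The people who stopped can best say which component failed them: the dermatoscope, the App, the web report or the reminders. A call for interest at the end of follow-up does nothing to reach them, and they may be less inclined to answer it than people who used the package throughout. Participants have also already opted into the trial, own a compatible smartphone and have a study partner, so this is a second layer of self-selection.

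At stake is what the pilot passes on to the larger trial described in section 5.2: a view of patient acceptability, and a list of things to change.

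**Working it through.** **What the plan computes.** There is no figure to reproduce for this sub-study, because the 30 rests on convention. The one calculated figure in section 13.1, a margin below 10% for the recruitment proportion, reproduces (1.96 × √(0.3 × 0.7 / 100) = 0.090) but has no bearing here.

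**Search for a selection rule.** Sections 6.2, 12.2 (M9), 13.1 and 13.5 were read together. None mentions purposive or maximum-variation sampling, a target by use or discontinuation, or a comparison of interviewed with non-interviewed participants. Expressed interest is the only rule given.

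**Is the needed information held?** Yes. Section 5.3 says data are collected through the web-based checker in the intervention group, and section 8.3 has text reports and images submitted through the web checker and the App. With prompts every 2 months over 6 months there are 6 / 2 = 3 rounds, so rounds submitted can be counted for each participant.

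**How far could the interview sample tilt?** Inputs from the documents: 50 in the arm (section 3) and 30 interviews (section 13.5). That is 30/50 = 60% of the arm, leaving 20 not interviewed. Assumed inputs: the number of stoppers *s*, and their volunteering rate *r* relative to the others. If the 30 places fill in proportion to volunteering,

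expected stoppers interviewed = 30 × *s* × *r* / [(50 − *s*) + *s* × *r*],

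with a floor of 30 − (50 − *s*) when fewer than 30 others are available.

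| Stoppers of 50 | Proportional share (0.6 × *s*) | *r* = 1/2 | *r* = 1/4 | *r* = 0 |
|---|---|---|---|---|
| 10 | 6 | 3.3 | 1.8 | 0 |
| 15 | 9 | 5.3 | 2.9 | 0 |
| 20 | 12 | 7.5 | 4.3 | 0 |
| 25 | 15 | 10.0 | 6.0 | 5 |

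For example, with *s* = 20 and *r* = 1/4: 30 × 5 / (30 + 5) = 4.3. At *r* = 1 every row returns the proportional share and there is no shortfall. The last row shows the limit that 30 of 50 imposes: with 25 stoppers, at least 30 − 25 = 5 must be interviewed to reach 30.

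**The case against.** The invitation covers everyone randomised to the intervention, not only current users, and any voluntary interview needs people to agree. The plan does not say how interviewees are picked from those interested, so purposive choice is unstated rather than ruled out. Interviewing 60% of the arm limits the distortion. Dissatisfied people may also volunteer. All of this stands, and it is why the point is worded as a possibility.

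A reader might infer that acceptability will be overstated by a calculable amount. With assumed acceptability of 90% in continuers and 30% in stoppers, 20 stoppers and *r* = 1/4, the interviews would show (25.7 × 0.9 + 4.3 × 0.3) / 30 = 81%, against (30 × 0.9 + 20 × 0.3) / 50 = 66% in the arm. The milder case of 10 stoppers, *r* = 1/2 and 80% against 50% gives an excess of about 3 points. The documents do not support using such figures as the size of the problem. Every rate is assumed, and section 13.5 plans Framework Analysis, which estimates no proportion.

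A reader might also infer that these volunteers are the only evidence on acceptability and barriers. They are not. Between 5 and 10 clinicians are interviewed, section 11.1 has App and dermatoscope difficulties recorded and reviewed by the trial management committee, and M2.1 and the web-checker data bear on use. None of these, however, gives a patient's own account of why they stopped. The acceptability item in section 12.2 concerns fewer scheduled visits, which is a different question.

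**Conclusion.** The point holds as a weakness in sampling. Selection by expressed interest, with no regard to use, leaves to chance whether people who stopped or rarely used the package are heard. The likely direction is a rosier picture of patient acceptability, but that requires stoppers both to volunteer less and to be less favourable. The documents establish neither. The size cannot be derived from them, and the counts in the table only show what plausible inputs would do.

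The main harm is qualitative: reasons for stopping, and components to change, may be missed. The primary outcome and the randomised comparisons are untouched. This is a cheap improvement to the sub-study.

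**What to change.** In section 13.5, replace selection by expressed interest with purposive invitation based on the web-checker and App records:

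- Group intervention participants by rounds submitted: none or one, two, three.
- Approach the low-use group first, including those who have stopped visits but accept phone contact (section 8.6.3).
- Set a target of about 10 low-use interviews, or all who agree if fewer, and fill the remaining places from the other groups. This should be a target and not a fixed quota: if 20 people were low users and 20% to 50% agreed, only 4 to 10 would come forward.
- Report the numbers invited and interviewed in each group, and present themes by level of use.

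The cost is an edit to section 13.5, with the ethics approval that section 16.2 requires for amendments, and invitations targeted from records already held. No extra interviews are needed. The downsides are more refusals and a little more coordinator time. Those who want no further contact remain out of reach, because section 8.6.3 ends all correspondence with them, and the report should say so.
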